15. Take an extra water pill extra_pill	1	2	3	4
16. Call your doctor or nurse for guidance call_dr	1	2	3	4

17. Think of a remedy you tried the last time you had trouble breathing or ankle swelling

	I did not try anything	Not Sure	Somewhat Sure	Sure	Very Sure
How sure were you that the remedy helped or did not help? sure_remedy	0	1	2	3	4

Self-Efficacy Related to Self-Care

SECTION C:

In general, how confident are you that you can do the following:

	Not Confident	Somewhat Confident	Very Confident	Extremely Confident
18. Keep yourself free of heart failure symptoms? free_sxs	1	2	3	4

19. Follow the treatment advice you have been given? follow_advice	1	2	3	4
20. Evaluate the importance of your symptoms? evaluate_sx	1	2	3	4
21. Recognize changes in your health if they occur? recognize_changes	1	2	3	4
22. Do something that will relieve your symptoms? relieve_sxs	1	2	3	4
23. Evaluate how well a remedy works? evaluate_success	1	2	3	4

Perceived Health Status

1. **How would you rate your overall health? **srh****
 - a. Excellent
 - b. Very good
 - c. Good
 - d. Fair
 - e. Poor

Health Status: Symptom Severity

Which one of the following statements best describes how your heart condition affects you today?
nyha_class

1. Usual physical activity does not cause fatigue, shortness of breath or chest pain. You have no difficulties with usual physical activity
2. Usual physical activity results in fatigue, shortness of breath or chest pain. You have some difficulty with usual physical activity.
3. Less than usual activity causes fatigue, shortness of breath or chest pain. You have great difficulty with usual physical activity.
4. You are unable to do any physical activity without discomfort. Fatigue, shortness of breath or chest pain may be present even at rest.

Communication with Provider

When you visit your doctor, how often do you do the following?

1. Prepare a list of questions for your doctor **make_list**

Never 0	Almost never 1	Sometimes 2	Fairly often 3	Very often 4	Always 5
------------	-------------------	----------------	-------------------	-----------------	-------------

2. Ask questions about your treatment [ask_questions](#)

Never 0	Almost never 1	Sometimes 2	Fairly often 3	Very often 4	Always 5
------------	-------------------	----------------	-------------------	-----------------	-------------

3. Discuss any personal problems that may be related to your illness [discuss_probs](#)

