4.1 Intervention/Treatment procedures (by visits)

PATIENT'S MEDICAL APPOINTMENT

The following protocol is for the administration of the study visit at the time of the patient's medical appointment.

Each dyad member will receive a prompt list to complete in the clinic waiting room immediately before their appointment. HF dyads will complete the prompt list without staff help. Completing the prompt list involves two steps. In step 1, participants will independently select from a list of questions or write in their own questions they would like to ask their health care provider during the visit. Patients will also be asked to select among a pre-determined list of behaviors they would like their family member to engage in during the visit (e.g., write down the providers instructions). In step 2, dyad members will collaboratively decide which questions to discuss during the visit. Participants will be encouraged to take the prompt list into the exam room and use it to facilitate communication with the HCP. The RA may take a picture of the prompt lists (which will not contain any identifying information, only a study id) to assess areas of agreement and disagreement between the dyad on what to discuss with the HCP.

The RA/SC will meet participants in the waiting room and introduce their self and review the directions of completing the prompt list with the participant(s) as well as the process of the data collection.

Note: If a participant has not completed an informed consent, one must be obtained prior to proceeding with the audio recorded medical appointment.

The RA/SC will obtain consent from the patient's HCP and remind the HCP that the appointment will be audio recorded. After the HCP has consented and the RA/SC has confirmed which exam room the patient will be in, the RA/SC can set up the audio recording equipment. When the HCP enters the room, the RA/SC will start the recording and exit the room. Once the appointment is over, the RA/SC will knock on the door and enter the exam room to stop the recording.

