3. I went into great detail about my medical symptoms [detailed_sxs2](#)

Strongly disagree									Strongly agree
0	1	2	3	4	5	6	7	8	9

4. I asked the doctor to explain the treatment or procedure in greater detail [explain_tx2](#)

Strongly disagree									Strongly agree
0	1	2	3	4	5	6	7	8	9

5. I offered opinions to the doctor [offer_opinions2](#)

Strongly disagree									Strongly agree
0	1	2	3	4	5	6	7	8	9

6. I expressed concerns to the doctor [express_concern2](#)

Strongly disagree									Strongly agree
0	1	2	3	4	5	6	7	8	9

Perceived Efficacy in Interacting with Doctor

Next, I'd like to ask you some questions about your interactions with your doctor.

1. **How confident are you in your ability to know what questions to ask a doctor?** *know_to_ask2*

Not at all confident 0	1	2	3	Very confident 4
---------------------------	---	---	---	---------------------

2. **How confident are you in your ability to get a doctor to answer all of your questions?** *get_answers2*

Not at all confident 0	1	2	3	Very confident 4
---------------------------	---	---	---	---------------------

3. **How confident are you in your ability to make the most of your visit with a doctor?** *maximize_visit2*

Not at all confident 0	1	2	3	Very confident 4
---------------------------	---	---	---	---------------------

4. **How confident are you in your ability to get a doctor to take your health concerns seriously?** *take_serious2*

Not at all confident 0	1	2	3	Very confident 4
---------------------------	---	---	---	---------------------

5. **How confident are you in your ability to get a doctor to do something about your health concerns?** *make_dr_act2*

Not at all confident 0	1	2	3	Very confident 4
---------------------------	---	---	---	---------------------

6. **How confident are you in your ability to ask a doctor questions?** *able_to_ask2*

Not at all confident 0	1	2	3	Very confident 4
---------------------------	---	---	---	---------------------

1-MONTH FOLLOW-UP PATIENT QUESTIONNAIRE

1-Month Follow-up Measures

1. Self-care behaviors (Same measure as at baseline)
2. Self-efficacy related to self-care (Same measure as at baseline)
3. Communication with provider (Same measure as at baseline)
4. Emotional support
5. Tangible support
6. Perceived efficacy in interacting with doctor

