6.2 Secondary Endpoint

Secondary outcomes include: 1) mean score on acceptability checklist; 2) mean score on self-care of heart failure index scores (maintenance, management, and confidence subscales); 3) mean score on caregiver contribution to self-care of heart failure index scores (maintenance, management, and confidence subscales); 4) mean score on perceived efficacy in patient-physician interactions score; 5) mean score on communication with physicians measure

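### One of three items in the patient communication score closely overlaps with the intervention, so part of any baseline-to-1-month gain may reflect receiving the study's list

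*Combined protocol and SAP*

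**What the plan says.** The baseline patient questionnaire (Section 4, Communication with Provider) opens with the stem "When you visit your doctor, how often do you do the following" and has three items, each scored from 0 (never) to 5 (always):

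- make_list: "Prepare a list of questions for your doctor"
- ask_questions: "Ask questions about your treatment"
- discuss_probs: "Discuss any personal problems that may be related to your illness"

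Section 4.1 (Intervention/Treatment procedures) describes the intervention: "Each dyad member will receive a prompt list to complete in the clinic waiting room immediately before their appointment". In its first step, "participants will independently select from a list of questions or write in their own questions they would like to ask their health care provider".

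The 1-month measures in Section 4.2 include "Communication with provider (Same measure as at baseline"). Section 10 places that call 1 month (plus or minus 7 days) after the study appointment.

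Section 6.2 lists, as the fifth secondary outcome, "mean score on communication with physicians measure". Section 6.3 plans paired t-tests of the change from baseline to 1 month and effect sizes to help plan later proposals, and it says that no hypotheses are being tested. Section 3.1 gives a single-group design. No section plans item-level results for this measure or says whether the study's own list counts towards make_list.

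**The concern.** Selecting or writing questions on a form just before the visit is close to what make_list asks about. The 2-day call strengthens the association: the title it uses for the form refers to preparing for the visit, and patients who do not recall the form are told that it looks like a list of questions for the doctor. A patient asked at 1 month about preparing lists could reasonably count it.

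With no comparison group, nothing in the design separates a higher make_list answer that reflects the supplied list from one that reflects a new habit. A rise in this item alone would raise the score even if patients asked no more questions and raised no more problems than before. Because the study disclaims hypothesis testing, the estimated change and its effect size are what this outcome delivers. A later trial could be sized on an effect that partly records handing out the list.

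**Working it through.** **Inputs.** From the documents: three items, each 0 to 5; the same items at both times; one group; no plan to report items separately. The documents give no expected change, SD or scoring rule for this measure, so there is no figure of theirs to reproduce. Three things are assumed: the score is the unweighted mean of the three items; the SD of change in that mean lies between 1.0 and 1.5; and the item shifts are illustrative. Section 6.3 does not name the denominator of its effect size, so the SD of change is used here.

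**Formula.** Let make_list change by *k* points on average and each of the other two items by *m*.

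- Change in the three-item mean = (*k* + 2*m*)/3
- Part contributed by make_list = *k*/3
- Share of the gain from make_list = *k*/(*k* + 2*m*)
- Change in the mean of the other two items = *m*

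**Contribution of make_list.**

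| Rise in make_list (*k*) | Points on the 0–5 score (*k*/3) | Standardised, SD 1.5 | Standardised, SD 1.0 |
|---|---|---|---|
| 0 | 0 | 0 | 0 |
| 1 | 0.33 | 0.33/1.5 = 0.22 | 0.33/1.0 = 0.33 |
| 2 | 0.67 | 0.67/1.5 = 0.44 | 0.67/1.0 = 0.67 |

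**Share of the gain when *k* = 1.**

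- *m* = 0: 1/1 = 100%
- *m* = 0.25: 1/1.5 = 67%
- *m* = 0.5: 1/2 = 50%
- *m* = 1: 1/3 = 33%

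**Why the three-item score cannot settle the matter.** Two quite different results give the same gain:

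- *k* = 2, *m* = 0: (2 + 0)/3 = 0.67
- *k* = 1, *m* = 0.5: (1 + 1)/3 = 0.67

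The mean of the other two items changes by 0 in the first case and 0.5 in the second. Showing both scores separates them.

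**Is there another measure that fills the gap?** The 2-day call has a six-item Patient Communication scale with no list-making item. It is not among the baseline measures, so it gives no pre-post change.

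**The case against.** A reader might infer that part of any gain is built in, and that a higher make_list answer shows only that the list was delivered. The documents do not support that, for four reasons.

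- The stem asks about usual frequency and sets no recall window. One list at one visit need not change the answer, and a patient may not regard a largely pre-written form as a list they prepared.
- Communication behaviours are a stated target of the study. If patients take up list-making, that is a real effect.
- The protocol requires no further clinic visit before the 1-month call, but it does not restrict routine care and gives no visit frequency. It cannot be said that the study visit is the only new experience most patients would have to report.
- Section 4 allows a baseline survey to be finished after a clinic visit or by phone within that week. The script after baseline points to a later appointment, so it is unclear whether this could be the intervention visit. If it could, make_list might already be raised at baseline, which would shrink the gain.

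The scope is also narrow. The listed companion baseline measures do not include communication with the provider. This is one secondary outcome in a feasibility pilot.

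All of this stands, and it limits the point to a possible contribution that could be zero. It does not remove the overlap between item and intervention, and it does not supply a way to tell the explanations apart. The argument that list-making may be a genuine gain is a good reason to keep the planned score, and an equally good reason to show make_list separately.

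**Conclusion.** The point holds as a possibility, for patients. Part of any gain in the communication score may reflect receipt of the study list, and the planned analysis would not show how much. Under an unweighted mean, the contribution is 0 if make_list does not move, 0.33 points for a 1-point rise and 0.67 for a 2-point rise. At an assumed SD of change of 1.0 to 1.5, that is a standardised change of 0 to about 0.67. The scoring rule, the shifts and the SDs are all assumptions; the documents show neither that the item will move nor by how much. Matching the fifth secondary outcome to this three-item measure rests on the similarity of their names and is the natural reading. The primary outcome, the enrolment percentage, is unaffected.

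**What to change.** In Section 6.3, keep the three-item score as planned and prespecify three additions:

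1. State how the score is computed.
2. Report the baseline-to-1-month change and effect size also for the mean of ask_questions and discuss_probs, the two items that the intervention does not supply.
3. Report make_list separately.

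Any claimed effect on communication, and any effect size carried into planning, should be read in light of both scores. If only the three-item score moves, the gain may reflect the supplied list or new list-making, and the report should say so.

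The cost is one extra score from data already collected. A two-item score is somewhat less reliable, which is one reason to show it beside the planned score rather than in its place. This is a cheap improvement.

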4.1 Intervention/Treatment procedures (by visits)

PATIENT'S MEDICAL APPOINTMENT

The following protocol is for the administration of the study visit at the time of the patient's medical appointment.

Each dyad member will receive a prompt list to complete in the clinic waiting room immediately before their appointment. HF dyads will complete the prompt list without staff help. Completing the prompt list involves two steps. In step 1, participants will independently select from a list of questions or write in their own questions they would like to ask their health care provider during the visit. Patients will also be asked to select among a pre-determined list of behaviors they would like their family member to engage in during the visit (e.g., write down the providers instructions). In step 2, dyad members will collaboratively decide which questions to discuss during the visit. Participants will be encouraged to take the prompt list into the exam room and use it to facilitate communication with the HCP. The RA may take a picture of the prompt lists (which will not contain any identifying information, only a study id) to assess areas of agreement and disagreement between the dyad on what to discuss with the HCP.

The RA/SC will meet participants in the waiting room and introduce their self and review the directions of completing the prompt list with the participant(s) as well as the process of the data collection.

Note: If a participant has not completed an informed consent, one must be obtained prior to proceeding with the audio recorded medical appointment.

The RA/SC will obtain consent from the patient's HCP and remind the HCP that the appointment will be audio recorded. After the HCP has consented and the RA/SC has confirmed which exam room the patient will be in, the RA/SC can set up the audio recording equipment. When the HCP enters the room, the RA/SC will start the recording and exit the room. Once the appointment is over, the RA/SC will knock on the door and enter the exam room to stop the recording.

After the recording has been stopped, the RA/SC will need to collect a copy of the completed prompt list from the participant. The copy can be provided as a carbon copy, a picture taken by a camera, a scanned copy, or a copy from the copy machine in the clinic. Scanned copies and pictures must be saved on a study approved computer in order to prevent loss of data. It is preferable to obtain a picture using the study iPad; pictures will be taken on the iPad and entered into the REDCap application.

Once the RA/SC has obtained a copy of the completed prompt list, the RA/SC will provide the participant(s) with their gift card(s) for completing their baseline questionnaire for the study. The RA/SC will also have each participant sign a gift card receipt which the RA/SC will keep track of all gift cards. The RA/SC will also schedule a time to call the participant(s) for their 2 day follow up call and confirm telephone contact information. After their appointment and scheduling their next visit, the RA/SC will thank the participant(s) for their time and exit the room.

The following script will be used after the patient's in person medical appointment and data collection has completed.

Thank you for allowing us to audio record your appointment. The next part of the study is for you to complete a telephone survey 2 days from today. This call should last approximately 20. I will call you at a time that works best for you.

What is the best telephone number where I can reach you?

Great, thank you!

When would you prefer I call you?

__ Morning __ Afternoon __ Evening __ Specific time _____

Again, we really appreciate you taking the time to participate in the study.

[if the participant did not receive their gift card for completing their baseline questionnaires, provide them with their gift card and obtain a signed gift card receipt from the participant]

[hand them the PiH Study informational and contact sheet & the answer prompt for the 2 day follow up call]

Here is our information and a sheet with answer responses for our call in 2 days. You can use the answer response sheet to help you answer the questions when we talk on the phone.

Please contact us if you have any questions or if your appointment has been rescheduled.

Thank you and I will be in touch soon.

Copy of the Patient Prompt List [Note- the family member prompt list exactly parallel's the patient prompt list]

Part 1: Questions for Your Heart Doctor

Below is a list of questions that people with heart failure might want to ask their doctor. You can select questions on this list that you may want to ask or you can write in your own questions.

Three easy steps for using the question list below:

Step 1. **Review** the questions under each topic.

Step 2. **Select** the questions that you'd like to ask your doctor during today's visit.

Step 3. If you'd like to ask your doctor questions that aren't on the list, **write** those questions in the blank spaces on page 3.

The person who came with you today also might have questions. He or she will complete a separate list.

Remember that doctors answer all kinds of questions, even ones that might seem embarrassing. Talking honestly with your doctor will help you to make the most of your visit.

Topic: Heart Failure	Step 2: Select Your Questions
What is heart failure?	
How is heart failure different from other heart problems (such as heart disease and heart attack)?	
What type of heart failure do I have?	
What caused my heart failure?	
How can someone prevent heart failure?	
What increases a person's risk of heart failure (such as family history)?	

Topic: Managing and Treating Heart Failure	Step 2: Select Your Questions
Can heart failure be cured?	
What are my treatment options?	
How can I prevent my heart failure from getting worse?	
What tools can I use to track my health (such as a pulse ox or food journal)?	
How can I manage my heart failure while also managing other conditions (such as diabetes or arthritis)?	
Medicine	
What medicines am I taking? What is the purpose of each one?	
How long will I need to take each medicine?	
What medicine interactions or conflicts should I know about?	
Are there any medicines that I can stop taking?	
What are the possible side effects of my medicines?	
Food and Diet	
What diet should I follow?	
What are healthy foods that I can eat?	
What are some high salt foods that I should avoid?	
How much water should I drink each day?	
Is it okay for me to eat meals at a restaurant?	
What programs can help me to eat healthy (such as Meals on Wheels)?	
Exercise and Movement	
Am I healthy enough to exercise?	

What kind of exercise should I do? How much should I do?	
Should I participate in a special exercise program (such as physical therapy or cardiac rehab)?	
Will walking (instead of using a wheelchair) make my heart failure worse?	
Weight Management	
What is a healthy body weight for me?	
Would losing weight reduce the number of medicines that I need to take?	
What is the best way for me to lose weight?	
Surgery and Other Treatments	
What are the surgical options for treating my heart failure (such as a heart transplant)?	
Am I healthy enough to have surgery for other problems (such as a knee replacement)?	
Will I need to use oxygen at home (daytime or nighttime)?	
What should I do if I'm using oxygen and the power goes out?	

Topic: Signs and Symptoms of Heart Failure	Step 2: Select Your Questions
What are the common signs and symptoms of heart failure?	
What are some uncommon signs and symptoms of heart failure?	
What are the signs that my heart failure is getting better or worse?	
What signs and symptoms should I tell my doctor about right away?	
What is the best way to deal with...	
...memory problems?	
...mood swings?	
...sleep problems?	
...chest pain?	
...feeling tired?	
...feeling dizzy?	
...trouble breathing?	
...swelling or bloating?	
...gaining weight?	
...fast heartbeat?	

Topic: Signs and Symptoms of Heart Failure	Step 2: Select Your Questions
...colds or infections that won't go away?	

Topic: Day-to-Day Life with Heart Failure	Step 2: Select Your Questions
Work and Career	
Am I healthy enough to work?	
What kind of work should I not do?	
Sleep	
How much sleep should I be getting?	
Why might I have trouble sleeping?	
How can I improve my sleep quality?	
Fun Activities	
Am I healthy enough to have sex?	
What outdoor activities are safe for me to do?	
What are some healthy recreational activities for me to participate in?	
Am I healthy enough to _____ [fill in your favorite activity]?	
Around My House	
Am I healthy enough to cook my own meals?	
Am I healthy enough to do chores in and around the house (such as cleaning or gardening)?	
Travel	
Am I healthy enough to drive on my own?	
Am I healthy enough to fly on an airplane?	

Topic: What To Expect with Heart Failure	Step 2: Select Your Questions
How bad is my heart failure?	
Can my heart failure get better?	
How long do most people with heart failure live?	
What can we do to help me live longer?	
What can we do to help me live more comfortably?	

What are my options when my heart failure gets really bad?	
How can I prevent other problems caused by heart failure (such as stroke)?	

Topic: Support for You and Your Family/Friends	Step 2: Select Your Questions
What support services are available through this health system?	
What support services are available in my community?	
Emotional Support	
How can I find a support group for people with heart failure?	
How can I find a support group for my caregiver, family members, or friends?	
What is the best way to tell my family and friends about my heart failure?	
Financial Support	
Who can help me with disability and unemployment benefits?	
How can I get help with insurance and medical bills?	
How can I get help affording my medications?	
Is there a way to reduce the cost of my current medications?	
Logistical Support	
Who can help me with transportation to and from medical appointments?	
Who can help me with transportation for other needs (such as running errands)?	
How can I find help with daily activities (such as cooking, running errands, etc.)?	
What types of adult daycare are available for me?	
Life Planning	
How can I help my family prepare if my heart failure gets really bad?	

Topic: Healthcare Team Roles and Responsibilities	Step 2: Select Your Questions
Who are the members of my healthcare team?	
What does each member of my healthcare team do? Who is responsible for what?	

Topic: Healthcare Team Roles and Responsibilities	Step 2: Select Your Questions
How can I find the right healthcare team if I'm moving to a new area?	
When should I...	
...call my heart doctor?	
...call my primary care doctor?	
...go to the hospital?	
...call 911?	

Step 3: Write Your Own Questions (Optional)	

Part 2: Help from Your Companion

Having a family member or friend accompany you to your medical appointment can be useful, especially if that person knows how to help. Below are some ways a companion might support you during your visit. Read through this list and put a checkmark next to the ways you'd like your companion to help.

✓	I would like my companion to...(check all that apply)
	Take notes on what the doctor says during my appointment.
	Remind me to ask my questions.
	Ask my doctor questions for me.
	Remind me to tell my doctor about my symptoms.
	Tell my doctor about my health.
	Make sure I understand what my doctor says.
	Stay in the waiting room for part of the visit.
	Other ways you would like your companion to help you: _____ _____ _____
	I don't need my companion to help me during my visit.

Once you and your companion have each completed your own forms, please compare the forms and decide together which concerns are most important to discuss with your doctor today.

